## **7.4 Criteria for Initiating Treatment**

### Inclusion criteria

No exacerbations during the run in. Patients, who exacerbate during the run-in, may re-enroll 4 weeks after the exacerbation has resolved (completed course of systemic corticosteroids).

Completed 1st bronchoscopy and absence of complications or serious adverse events following the procedure (i.e. hospitalizations)

## **8 STATISTICAL ANALYSIS AND POWER CALCULATIONS**

### **8.1 Sample Size Determination**

To ensure 90% power to detect a difference in the change in the methacholine dose required to produce a PC20 before and after treatment, a sample size of n=12 participants will be required. This estimate assumes an alpha level of 0.05, and a 2-sided test. The estimate of variability and effect size used was by McRedmond et al, in which the PC20 effect size associated with CLA administration was 3.8 (SD 1.9). There are no preliminary data on how CLA or NOx + CLA affect exhaled NO and therefore are unable to reasonably anticipate a sample size for adequate power.

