### 5.2 Description of the Study Design

Potential subjects will be recruited from the Asthma Institute registry and the CTSI registry, and throughout the community at large. After an initial screen visit, those who sign the consent and meet eligibility will proceed to have methacholine testing; subjects with a > 12% bronchodilation in FEV1, or achieving a 20 % reduction in FEV1 from baseline (PC20) after methacholine, will receive **NOx + CLA** for a period of 8 weeks.

\* 15Nox dose will be taken 24 hours prior to V6 bronchoscopy

\*\*An additional visit might be needed in some participants to perform pre- and post-spirometry after an adequate medication withhold

Prior to treatment, participants will undergo a baseline bronchoscopy at UPMC Montefiore, after which they will be instructed to begin taking the assigned intervention for 8 weeks. At the completion of the treatment period, participants will undergo a second methacholine challenge and a final bronchoscopy.

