### **7.2 Inclusion Criteria**

- 1) Adequate completion of informed consent process with written documentation
- 2) Male and female patients, ≥ 18 - 65 yrs old
- 3) Diagnosis of asthma: based on previous physician diagnosis and either baseline pre-bronchodilator FEV1 50% or greater predicted with a 12% or greater

bronchodilator response to 4 puffs of albuterol or PC20 methacholine (16 mg) if no BD response. If the subject is not currently on an ICS or ICS-LABA combination, PC20 should be < 8 mg, if no BD response. Spirometry results within the prior 24 months located in the subject's medical records can be used to determine eligibility, if available.

- 4) From all racial/ethnic backgrounds with a diagnosis of asthma for  $\geq 6$  months;
- 5) Smoking history  $\leq 10$  pack years and no smoking in the last year;
- 6) BMI  $\geq 30$
- 7) If subject is on ICS or ICS/LABA therapy- 30 days on a stable dose (up to 1,000 mcg daily fluticasone equivalent)

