## **8.3 Efficacy Analyses**

Primary analysis: The primary analysis will test whether there is a significant difference in exhaled NO and measures of airway oxidative stress (superoxide production, XO activity in biopsies) before and after taking either of the intervention arms. This analysis will utilize an approach of comparing average values pre and post intervention, using matched paired comparisons.

Matched analysis are very efficient in controlling for confounders, as the analysis uses the same individual as case and control under different treatment conditions. Secondary outcomes will be tested following the same scheme of pre and post matched comparisons. To determine the relevance of measured variables, these will be compared to results from healthy controls undergoing bronchoscopy as part of the Electrophilic Fatty Acid Derivatives in Asthma (EFADA) study (IRB#: PRO11010186). This analysis will allow cross sectional comparisons and determine, for example, how obesity influences some of the baseline study variables.

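### The trial is sized on raw methacholine PC20, but the plan gives no scale, top dose or rule for patients whose FEV1 never falls 20%, and missing-at-random does not cover them.

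*Combined protocol and SAP*

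**What the plan says.** Section 8.1 sizes the trial on the pre/post change in "the methacholine dose required to produce a PC20 before and after treatment". It cites an effect of 3.8 (SD 1.9), 90% power and a two-sided alpha of 0.05, and concludes that "a sample size of n=12 participants will be required". Section 2 shows where 3.8 comes from: a placebo-controlled CLA trial with mean changes of 5 mg/ml and 1.2 mg/ml, so 5 - 1.2 = 3.8 on the raw scale. No log or doubling-dose scale appears anywhere.

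Section 8.3 describes one approach, "comparing average values pre and post intervention, using matched paired comparisons", and applies it to the primary variables and to the secondary outcomes.

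Entry does not require a PC20. Section 5.2 treats "subjects with a > 12% bronchodilation in FEV"1 or those who reach a 20% fall on methacholine. Section 7.2 asks for "PC20 methacholine (16 mg) if no BD response", and for a value below 8 mg in patients with no bronchodilator response who are not on ICS or ICS-LABA. The 16 mg is an eligibility limit; no top dose is given for the challenge itself. Section 6 (Visits 2 and 5) stops the challenge if and when FEV1 has fallen 20%, and does not say what is recorded if it never does.

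Section 8.5 covers dropouts and missed visits with likelihood methods under missing-at-random. It allows non-ignorable models if that assumption looks unreasonable.

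**The concern.** PC20 is measured only up to the highest dose given. A patient who does not react by then has a PC20 above that dose, which is information and not a gap. This can happen in two ways.

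- **After treatment.** A patient who improves enough no longer reaches a 20% fall. If that pair is left out, a large improvement is lost and the average change moves toward zero.
- **At baseline.** A bronchodilator responder may have no baseline PC20. If that patient reacts after treatment, airway responsiveness has worsened, and a complete-pair analysis would not show it. Section 9.1.1 says the challenge is done mainly to detect such worsening.

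In both cases the value is unobserved because of its size, so missing-at-random does not apply.

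Scale adds to the problem. Methacholine is given in increasing doses, so a difference in raw units is dominated by the least reactive patients, who are also the ones closest to the top dose.

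At stake are the hyperresponsiveness result, its use as a safety check, and the meaning of the only power statement in the protocol.

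**Working it through.** **1. The plan's own figure.** Inputs from Section 8.1: difference 3.8, SD 1.9, two-sided alpha 0.05, power 90%.

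- Two-arm normal formula: n per arm = 2 × (1.960 + 1.282)² × (1.9/3.8)² = 2 × 10.51 × 0.25 = 5.25, rounded up to 6, so 12 in total. This reproduces n=12.
- Single-arm paired test, taking 1.9 as the SD of the paired change: d = 3.8/1.9 = 2. The normal formula gives 10.51 × 0.25 = 2.63, so 3 pairs. The paired t test needs 5 pairs (power 0.909).

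So 12 is the total for a two-arm comparison, not the size needed for the paired design. That is a separate matter, but it explains the slack below.

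**2. Pair loss on the plan's own inputs** (noncentral paired t, d = 2):

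| Usable pairs | Power |
|---|---|
| 12 | >0.999 |
| 8 | 0.998 |
| 6 | 0.971 |
| 5 | 0.909 |
| 4 | 0.755 |

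Even if exactly the 6 largest of 12 changes are removed, the mean falls from 3.80 to 2.38 and power is 0.918. If half the patients lack a baseline PC20 at random (assumed log-normal baseline, geometric mean 2 to 8, geometric SD 2.5, cap 16), power is 0.81 to 0.89, because some trials end with fewer than 5 pairs. With 30% lacking one it is 0.96 to 0.99.

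**3. Dependence on the SD.** With 12 pairs, 90% power needs d = 1.029, so the SD of the change may be at most 3.8/1.029 = 3.69. At SD 3.7, power is 0.90 with 12 pairs, 0.77 with 9 and 0.53 with 6. Section 2 prints 1.9 in brackets without a label, so it is not certain that it is the SD of a paired change.

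**4. A multiplicative effect.** The documents give no PC20 distribution, so these inputs are assumptions: true log2 PC20 normal with between-patient SD 1.5; within-patient SD 0.75 doublings at each visit; entry at observed PC20 of 16 or less; a true gain of one doubling; values above 16 unobserved. There were 4,000 simulated trials of 12 patients per setting (simulation error about √(0.5 × 0.5/4000) = 0.8 points).

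| | Median 4 mg/ml | Median 8 mg/ml |
|---|---|---|
| Usable pairs of 12 | 9.7 | 7.9 |
| Power, raw paired t, complete pairs | 54% | 45% |
| Power, raw paired t, if every value were known | 65% | 78% |
| Power, log2 paired t, complete pairs | 67% | 52% |
| Power, log2 capped at 16 | about 87% | about 87% |
| Mean log2 change, complete pairs (true 1.0) | 0.88 | 0.82 |

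The raw rows show that scale alone costs power before any pair is lost.

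**5. Limits of the simple repairs.** Putting non-reachers at the next doubling overshoots: it averages 1.13 and 1.21 against a true 1.0. With no true effect it rejects about 6% and 8% of the time. At median 8, a capped log2 or signed-rank test rejects about 6% to 7%. The cause is entry on an observed baseline PC20, which brings regression to the mean. Capping also understates the change, since every unreached value is set below its true level.

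**The case against.** A reader might infer that the plan discards the best responders. It does not say so. Leaving pairs out is the natural default for a paired mean, but no section states that an unreached PC20 is dropped, capped or censored, and Section 8.5 promises likelihood methods. The silence is the defect. The promise does not cure it: a likelihood method is valid here only if it models the censoring. The non-ignorable fallback in 8.5 is left to later judgement, although this form of missingness is known in advance.

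A reader might also infer that the 90% power is broken. The documents do not support that. On 3.8 (SD 1.9), pair loss alone leaves 90% down to 5 pairs. The 45% to 55% figures need a multiplicative effect and a spread that the protocol does not give, and part of that shortfall comes from scale, not from lost pairs. The simulation also admits everyone up to 16, although Section 7.2 sets a limit below 8 mg for some patients, so it overstates their losses. It gives every patient a baseline PC20, so it does not measure loss at baseline.

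Finally, PC20 is not in Section 4.1, in the list in Section 4.2, or among the primary variables of Section 8.3, and Section 9.1.1 calls the challenge primarily a safety measure. That stands, and it limits the reach of the point. But PC20 is the sole basis for n=12, Section 8.4 commits to monitoring hyperresponsiveness, and the abstract names it as an effect to be determined.

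**Conclusion.** The point holds in limited form. The plan sizes the trial on raw PC20, describes only paired averages, and has no rule for a PC20 that is not reached at either visit. The missing-at-random assumption fails for a value above the top dose. If pairs lost after treatment are left out, the estimated change is biased toward no effect: about 0.8 to 0.9 of a true doubling, with about 8 to 10 of 12 pairs usable, under the assumptions in step 4. Raw complete-pair power is then about 45% to 55%, against about 87% for capped log2.

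The primary analysis of exhaled NO, superoxide and XO activity is unaffected. The stated 90% is not shown to fail from pair loss alone. It becomes fragile if the SD of the paired change is near 3.7 instead of 1.9, if the effect is multiplicative, or if about half the patients lack a baseline PC20. The documents quantify none of these.

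**What to change.** Add a short paragraph on PC20 to Section 8:

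- Analyse PC20 on the log2 (doubling-dose) scale, in one stated unit; the text now mixes mg and mg/ml.
- State the top dose used in the analysis.
- Treat an unreached PC20 at either visit as right-censored at that dose, using censored (Tobit-type) regression for paired data. Alternatively, use a signed-rank test: a change from measured to unreached counts among the largest improvements, the reverse among the largest worsenings, and unreached at both visits as no change. Exclude these patients from the missing-at-random provision in 8.5.
- Report how many patients have a measured PC20 at each visit.
- State in 8.1 that the power figure applies to patients with a baseline PC20.

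The cost is SAP wording and a little more analysis, with no new data or visits. The effect is reported in doubling doses instead of mg/ml. With 12 patients a censored model may be imprecise, so one method should be named as the main one in advance. Because entry can depend on the observed baseline PC20, some regression to the mean remains under any of these methods and should be noted when the change is interpreted.

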## ABSTRACT

Obesity is an asthma comorbidity associated with increased severity, poor control, reduced steroid responsiveness and greater exacerbation and healthcare utilization rates. These associations are not explained by having a greater degree of Th-2 inflammation. Rather, the obese asthma phenotype defined in several cluster studies, has paradoxically reduced levels of Th-2 biomarkers, including sputum eosinophils and exhaled nitric oxide (NO). Our previous research has shown that the inverse relation between increased body mass index (BMI) and reduced exhaled NO, may be explained by a metabolic imbalance characterized by lower L-arginine and greater asymmetric di-methyl arginine (ADMA) levels. Having a low L-arginine/ADMA ratio has been shown to inhibit and uncouple all isoforms of nitric oxidase synthase (NOS), thereby reducing NO bioavailability and promoting oxidative stress through enhanced superoxide production. In obese asthmatics, this imbalance not only correlates with exhaled NO, but also with lower FEV1% and poorer asthma-related quality of life. Yet the effect of obesity in asthma is unlikely to be solely dependent on a single mechanism. Other factors, such as increased Th1 and Th-17-mediated inflammation have been shown to occur in human and animal models. Given all of these potential avenues, it is imperative that an intervention is sufficiently pleiotropic that can, in addition to restoring airway NO levels, also reduce other obesity-related non-Th2 mechanism of inflammation. We hypothesize that treatment with conjugated linolenic acid (CLA) + nitrate and nitrite (together known as NOx), will restore NO airway bioavailability, reduce oxidative stress and improve airway inflammation in obese asthmatics. To test this hypothesis, we propose a phase II pilot study in which obese asthmatics, will be treated orally with CLA+NOx for 8 weeks, in an open label study design to assess pre to post-intervention changes in airway and systemic biomarkers, and to determine the effects on lung function and bronchial hyperresponsiveness. Participants will undergo a pre and post intervention bronchoscopy. The results obtained from this project will be greatly informative to our understanding of the obese – asthma pathophysiology and for the development of clinical trials to determine the potential benefit of this intervention in improving health outcomes.

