**Additional treatments focusing on inflammatory and oxidative pathways are needed to improve the health of obese asthmatics with metabolic syndrome.** Several of the pharmacological properties of nitrite, nitrate and CLA make them ideal candidates to overcome many of the metabolic and inflammatory factors associated with obesity, especially when coexisting with MS. For example, nitrate has been shown to improve endothelial function, reduce blood pressure and insulin resistance in diabetic patients (32). Another relevant aspect of NOx therapy is that it may increase airway NO bioavailability by providing an alternative source of NO other than NOS, which could be particularly useful in situations, such as obesity, when the L-arginine/ADMA balance favors iNOS uncoupling. CLA is a polyunsaturated fatty acid found in dairy products and ruminant meat (i.e. beef) and an average American diet supplies 15-174 mg of CLA daily. Moreover, CLA is formed in the body following conversion of linoleic acid to CLA by bacteria of the gastrointestinal tract. CLA has pleiotropic anti-inflammatory actions, including partial PPARγ agonist activity, NF-κB inhibition and Nrf2 activation. Clinically, CLA has been associated with a wide range of salutary effects including: decreased body fat mass in obese and healthy overweight patients (33, 34), decreased the leptin/adiponectin ratios, and reduced risk of colorectal cancer. Of particular relevance to obesity and asthma, CLA has been shown to suppress Th-1 and Th17-mediated inflammatory responses in dendritic cells (14). This effect could be relevant to obese late-onset asthmatics who have a greater Th1 polarization and in whom Th17 responses appear to play a major role. Also, its ability to decrease the leptin/adiponectin ratio could ameliorate airway inflammation. Clinically, CLA has been shown to be potentially effective in improving bronchial hyperresponsiveness in obese and overweight mild asthmatics randomized to receive CLA 4,560 mg/d for 12 weeks. Compared to placebo,

those receiving CLA, had a significant reduction in the average methacholine dose to achieve a 20% reduction in FEV1 (change in methacholine dose from pre to post treatment was 5mg/ml [1.9] in the CLA arm vs 1.2 [1.2] in the placebo, p=0.02). Interestingly, this occurred in the absence of any significant changes in systemic biomarkers of airway inflammation; however, the study did not include any airway measurements (10).

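### Section 8.1 powers a single-arm before/after PC20 test with a placebo-subtracted effect (3.8 = 5 − 1.2), so its n and power do not describe that test, and a significant change cannot by itself be credited to CLA + NOx

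*Combined protocol and SAP*

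**What the plan says.** Section 8.1 sets its aim as "To ensure 90% power to detect a difference in the change in the methacholine dose", compared before and after treatment, and concludes that "a sample size of n=12 participants will be required". It adds: "This estimate assumes an alpha level of 0.05, and a 2-sided test". The planning values come from a published CLA trial, "in which the PC20 effect size associated with CLA administration was 3.8 (SD 1.9").

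Section 2 describes that trial. Participants were "randomized to receive CLA 4,560 mg/d for 12 weeks" or to placebo, and the pre-to-post changes in methacholine dose were "5mg/ml [1.9] in the CLA arm vs 1.2 [1.2] in the placebo, p=0.02". Section 2 does not say what the bracketed figures are; 8.1 calls the 1.9 an SD.

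The present trial is open label with one treated group (sections 5.1 and 5.2). Section 8.3 plans matched pre/post comparisons and gives no reference value for the change. The healthy EFADA controls serve only for cross-sectional comparison.

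**The concern.** The arithmetic 5 − 1.2 = 3.8 identifies the planning effect as a between-arm contrast, that is, the improvement with CLA over and above placebo. Section 8.1 attaches it to a "difference in the change in the methacholine dose required to produce a PC20 before and after treatment", which has no placebo arm to subtract. The effect size belongs to one comparison and the test to another.

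Two things follow. First, the stated n and power may not describe the test that will be run. Second, PC20 is the only measure with a sample-size calculation, and the abstract says the trial is "to determine the effects on lung function and bronchial hyperresponsiveness". A significant before/after change could then be read as the placebo-adjusted effect that 8.1 names, although nothing in the design removes the change seen without active treatment.

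**Working it through.** **Inputs.** From 8.1: effect 3.8, SD 1.9, two-sided alpha 0.05, power 90%, n=12. From section 2: CLA change 5 [1.9], placebo change 1.2 [1.2], p=0.02. The size of the source arms is not given.

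**1. Reproducing n=12.** (1.960 + 1.282)² ≈ 10.51 and (1.9/3.8)² = 0.25.
- Two groups, normal approximation: n per arm = 2 × 10.51 × 0.25 = 5.25, so 6 per arm and 12 in total. Power at 6 per arm is 93.4% by the normal approximation and 87.6% by exact t. Exact t needs 7 per arm, 14 in total.
- Paired, one group, normal approximation: n = 10.51 × 0.25 = 2.63, so 3. The exact noncentral t gives 75.5% at n=4 and 90.9% at n=5, so 5.
- Paired, if 1.9 were a per-visit SD with zero correlation: SD of change = 1.9 × √2 = 2.69, and exact t needs 8.

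Of these, only the two-group total gives 12.

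**2. Power of the paired test at n=12.** Noncentrality = (effect/SD) × √12.
- Effect 3.8, SD 1.9: 6.93, power above 99.9%.
- Effect 5, SD 1.9: 9.12, power above 99.9%.
- For n=12 to give 90% power at 3.8, the SD of the change would have to be about 3.69.

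**3. Is 1.9 an SD?** Equal arms of size m are assumed.
- Brackets as SDs: t = 3.8/√((1.9² + 1.2²)/m). This gives p = 0.015 at m=4 and 0.0003 at m=8.
- Brackets as standard errors: t = 3.8/√(1.9² + 1.2²) = 1.69. This gives p of about 0.10 to 0.11 for m from 8 to 20.

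Neither reading fits p=0.02 at plausible arm sizes, so the label has to be confirmed from the source. It matters. If 1.9 is a standard error, then SD = 1.9√m, and power at n=12 for a true change of 5 against zero is 83% (m=8), 67% (m=12) or 46% (m=20).

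**4. Chance of a significant result when the drug adds nothing and the true change is 1.2.** Two-sided paired t-test, n=12, 11 df, critical value 2.201, null of zero.

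| SD of change | Basis | Significant |
|---|---|---|
| 1.9 | as stated in 8.1 | 51.4% |
| 1.2 | placebo bracket read as an SD | 88.3% |
| 2.69 | 1.9 per visit, zero correlation | 29.3% |
| 3.39 to 5.37 | placebo bracket as a standard error, m = 8 to 20 | 20.1% to 10.9% |
| 5.37 to 8.50 | CLA bracket as a standard error, m = 8 to 20 | 10.9% to 7.3% |

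**5. What the interval can show.** At SD 1.9 and n=12 the 95% CI half-width is 2.201 × 1.9/√12 = 1.21. An observed mean change above about 1.2 + 1.21 = 2.41 would therefore place the whole interval above 1.2.

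**The case against.** The strongest reply is that the protocol promises little about PC20. It is not among the outcomes in sections 4.1 to 4.3. The primary analysis in 8.3 concerns exhaled NO, superoxide and XO activity. Section 9.1.1 says the challenge is done mainly for safety. No rule for claiming a PC20 benefit is written down, and the zero null is implied rather than stated. This stands and limits the reach of the point. It does not remove it, because 8.1 rests the sample size on PC20 alone and the abstract names hyperresponsiveness as an effect to be determined.

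A reader might infer that the type I error is inflated to 51–88%. The documents do not support that. If the true mean change is 1.2, the hypothesis of zero change is false, and rejecting it is correct. Those figures are power to detect a real change that the drug did not cause. The 88% end also depends on an unlabelled bracket.

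A reader might infer that using 3.8 leaves the trial underpowered. It does not: against zero, 3.8 is smaller than 5 and so conservative. Any shortfall would come from 1.9 being a standard error, which is unverified.

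It is also tempting to replace the null with 1.2. That restores 5% only if the non-drug change is exactly 1.2. If 1.9 is a standard error, moving the null would cut power for a true change of 5 from 83% to 61% (m=8) or from 46% to 29% (m=20). The 1.2 comes from a 12-week study of obese and overweight mild asthmatics, whereas this trial lasts 8 weeks and requires BMI of at least 30. It can serve as a benchmark but is too uncertain to be a fixed null.

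**Conclusion.** The point holds in limited form. Section 8.1 describes a placebo-subtracted contrast as the effect for a before/after test. Its n=12 at 90% power matches a two-group total and not the paired test, whose power at n=12 exceeds 99.9% on 8.1's own inputs. That a two-group calculation was carried over is the likely explanation, but the documents do not say so.

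Separately, a significant PC20 change against zero would not show an effect of CLA + NOx beyond placebo. With a non-drug change of 1.2, significance would occur in about 51% of trials at the stated SD. The range across readings is about 7% to 88%, depending on what the brackets are and on the assumed source arm size.

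This affects how the PC20 result is read and how the sample size is justified. It does not touch the planned primary analysis of exhaled NO and oxidative stress.

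**What to change.** In 8.1:
- State that 3.8 is a CLA-minus-placebo difference, and give 5 as the corresponding before/after change.
- Confirm from the source whether 1.9 is an SD or a standard error.
- Restate the power of the paired test at n=12 on that basis.

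In 8.3:
- Add the PC20 analysis, keeping the paired test against zero.
- Report the mean change with its 95% CI among participants with a PC20 at both Visit 2 and Visit 5, and say how many lack one. Entry on bronchodilator response means that some may have no baseline PC20.
- Show the cited placebo change of 1.2 mg/ml as an external benchmark. Do not attribute an improvement to CLA + NOx unless the whole interval lies above 1.2.
- Say that the benchmark is itself uncertain and does not replace a control arm.

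The cost is a few sentences and one look at the cited paper, with no added patients, visits or measurements. The downside is a more cautious PC20 claim.

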## 5 RESEARCH DESIGN AND METHODS

### 5.1 Study Design

This is an open-label, single center, proof of concept pilot study in obese asthmatics.

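### Section 8.1's n=12 for 90% power does not follow from its own inputs: a single-arm paired design needs 5, and 12 pairs give over 99.9%

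*Combined protocol and SAP*

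**What the plan says.** Section 8.1 states that, for 90% power at a two-sided alpha of 0.05, "a sample size of n=12 participants will be required". The target is "a difference in the change in the methacholine dose required to produce a PC20 before and after treatment". The inputs come from a cited CLA trial ("the PC20 effect size associated with CLA administration was 3.8 (SD 1.9"). For exhaled NO, the authors say they "are unable to reasonably anticipate a sample size for adequate power".

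The design has one treatment and no control arm. The Abstract says participants "will be treated orally with CLA+NOx for 8 weeks, in an open label study design to assess pre to post-intervention changes", and Section 5.1 says "This is an open-label, single center, proof of concept pilot study in obese asthmatics". Section 8.3 compares pre- and post-intervention means within person, and it applies the same paired scheme to the secondary outcomes. It also describes the comparison as "before and after taking either of the intervention arms", although there is only one arm.

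Section 2 gives the cited trial's result: "change in methacholine dose from pre to post treatment was 5mg/ml [1.9] in the CLA arm vs 1.2 [1.2] in the placebo, p=0.02". The bracketed values are not labelled there; Section 8.1 calls 1.9 an SD.

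**The concern.** A ratio of 3.8 to 1.9 is two standard deviations. A paired test on an effect that large needs only a handful of participants, so 12 at 90% power looked wrong for this design. The value 3.8 also looked like a difference between arms rather than a within-person change.

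No other justification is given for the trial's size. If the 90% figure belongs to a different comparison, Section 8.1 explains neither why 12 are needed nor what change 12 pairs can detect. That matters most for exhaled NO and the oxidative stress measures, which 8.3 makes the primary analysis and for which no power is given.

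**Working it through.** **Inputs.** Effect 3.8, SD 1.9, two-sided alpha 0.05, power 90%, n=12 (all Section 8.1). One arm, pre/post (Abstract, 5.1). Paired comparison (8.3). CLA change 5 [1.9], placebo change 1.2 [1.2] (Section 2).

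**Trying to reproduce 12 for the design described.** With d = mean change / SD of change, the paired t-test has power P(T > t at 0.975 on n-1 df), where T is noncentral t with noncentrality d√n. Here d = 3.8/1.9 = 2.0.

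- n=4: noncentrality 4.00, power 75.5%
- n=5: noncentrality 4.47, power 90.9%
- n=6: noncentrality 4.90, power 97.1%
- n=12: noncentrality 6.93, power 99.999%

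The required number is 5, not 12.

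**Other paired readings.** If 1.9 is a per-visit SD (an assumption), the SD of the difference is 1.9√(2(1-r)), where r is the correlation between visits.

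| Reading | SD of difference | d | n for 90% power |
|---|---|---|---|
| 3.8, per-visit SD, r=0 | 2.69 | 1.41 | 8 (92.7%; n=7 gives 87.4%) |
| 3.8, per-visit SD, r=0.25 | 2.33 | 1.63 | 7 (94.6%; n=6 gives 88.7%) |
| 3.8, per-visit SD, r=0.5 | 1.90 | 2.00 | 5 (90.9%) |
| Within-arm change 5, SD of change 1.9 | 1.90 | 2.63 | 4 (92.3%; n=3 gives 65.5%) |

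At r=0, 12 pairs still give 99.3% power. A Wilcoxon signed-rank test at d=2.0 needs 7 (by simulation), and a Bonferroni alpha from 0.05/2 to 0.05/10 needs 6 to 9. Reaching 12 from 5 through attrition would take a loss of 1 - 5/12 = 58%, and 8.1 states no attrition rate.

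**Where 12 does appear.** The two-group normal approximation gives n per arm = 2(1.960 + 1.2816)²/2.0² = 5.25, so 6 per arm and 12 in total. A two-sample t-test gives 87.6% at 6 per arm and needs 7 per arm (92.9%). The 6 + 6 match therefore holds only for the normal approximation with SD 1.9 in both arms.

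**Source of 3.8.** From Section 2, 5 - 1.2 = 3.8, which is the CLA-minus-placebo contrast. The within-arm change, which is what a single-arm trial estimates, is 5.

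**What 12 pairs can detect.** Solving the paired t power for d:

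| Evaluable pairs | d at 90% power | d at 80% power |
|---|---|---|
| 12 | 1.03 | 0.89 |
| 10 | 1.15 | 1.00 |

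**The case against.** **It changes nothing.** On the stated inputs 12 exceeds 5, so at least 90% power is achieved, and this is a pilot. That is true, and the point does not claim a shortfall. What remains is that the stated requirement is not a requirement, and nothing else in the plan supports the number.

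**The two-group origin is a guess, and other routes to 12 exist.** With the two spreads in Section 2 (1.9 and 1.2), a two-group calculation gives 4 or 5 per group, not 6. From the per-visit reading at r=0, n=8 with 33% loss gives 12. A Wilcoxon test on that reading needs about 9, and 9/(1 - 0.25) = 12. The plan states none of these allowances, so they do not rescue 8.1. They do show that the origin cannot be settled from the documents. The mismatch between a between-arm effect and a single-arm trial stands either way.

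**The SD itself is doubtful.** This is the strongest objection. Assume an unadjusted two-sample t-test with equal arms. If the brackets in Section 2 are SDs, p is 0.043 at 3 per arm and 0.015 at 4, so the quoted p=0.02 fits only about 4 per arm. If they are standard errors, t = 3.8/√(1.9² + 1.2²) = 1.69 and p is about 0.10 to 0.11 (source arms of 8 to 15, assumed), which does not fit either. Under the standard-error reading, the paired n for 3.8 would be 24 to 42, and 12 pairs would give about 37% to 61% power. So calling the error conservative depends on 1.9 being an SD, as 8.1 says. This is a reason to check the source; it does not show underpowering, and it does not restore 12.

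**The plan names no t-test.** Section 8.3 specifies only a paired comparison of means, and 8.5 mentions likelihood-based methods. A paired t-test is the natural planning test for 8.3, but the fix should name it as the basis of the figures.

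**Conclusion.** The concern holds. For the comparison the trial makes, 8.1's inputs give n=5 (90.9% power), and 12 pairs give over 99.9%, not 90%. If 1.9 is a per-visit SD with uncorrelated visits, the figures are n=8 and 99.3%. The effect of 3.8 is a between-arm difference that this trial cannot estimate; using it instead of 5 is cautious in size but is not the quantity tested.

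These results rest on 1.9 being an SD, as 8.1 states, and on a two-sided 5% paired t-test. The 6 + 6 explanation is likely but unconfirmed. The detectable effects in SD units do not depend on what 1.9 is. This should be fixed, but it does not threaten the trial.

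**What to change.** Keep n=12 and replace the 90% claim in 8.1 with: *With 12 evaluable pairs, a two-sided 5% paired t-test has 90% power for a mean change of 1.03 SD of the paired difference (0.89 SD at 80%); with 10 pairs, 1.15 SD at 90%.* This covers PC20, exhaled NO and each other outcome tested one at a time by the paired scheme in 8.3.

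Then:

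- Verify in the cited source what 1.9 is.
- Give power for PC20 itself only from the within-arm change and its verified SD, with the formula stated.
- Count that power on pairs with an evaluable PC20 at both visits. Sections 5.2 and 7.2 let participants qualify on bronchodilator response, so some may not reach a 20% fall, and 8.5 expects missing data.
- Correct the multi-arm wording in 8.3 ("before and after taking either of the intervention arms") to refer to the single intervention.

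The cost is protocol wording only. The downside is that PC20 power may look less favourable once the SD is verified.
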